ClinicalTrials.gov Document Upload

DOCUMENT DATE (IRB APPROVAL):

03-Jan-2024

NCT NUMBER:

NCT05938816

OFFICIAL STUDY TITLE:

Feasibility and acceptability of stress induction, physiological data collection, and Mindfulness-Based Stress Reduction among combat veterans with PTSD

INVESTIGATOR NAME:

[name], MCR

ORGANIZATION:

Oregon Health & Science University

1) Protocol Title

Feasibility and acceptability of stress induction, physiological data collection, and Mindfulness-Based Stress Reduction among combat veterans with PTSD

2) Objectives

Objectives are to gather feasibility and acceptability of key study elements (e.g., stress induction via cognitive stressor, physiological data collection including respiration, blood pressure, and heart rate, and the target intervention Mindfulness-Based Stress Reduction) among combat veterans experiencing PTSD symptoms to support a future K23 grant resubmission. Specific Aims are as follows:

Aim 1: Assess feasibility and participant acceptability of intervention and randomization procedures.

Aim 1A: Examine acceptability of MBSR via qualitative data gathered during a post-intervention focus group.

Aim 1B: Assess feasibility of recruiting and acceptability of randomizing participants to an MBSR or active control condition. Recruitment, differential retention, and home practice completion rates will be examined.

Aim 2: Assess feasibility and participant acceptability of concurrent stress induction and physiological data collection (i.e., systolic [SBP] and diastolic [DBP] blood pressure) procedures.

Aim 2A: Evaluate feasibility of stress induction via significant change in BP from baseline to stressor.

Aim 2B: Examine acceptability of physiological data collection concurrent with stressor task via focus group.

Aim 3: Evaluate sensitivity and responsiveness to change of outcome measures. Examining these qualities and pre-post changes in physiological and psychological resilience and PTSD symptoms will provide crucial information regarding relationships between the intervention and changes in relevant variables.

3) Background

Posttraumatic stress disorder (PTSD) is a significant public health concern¹ that negatively impacts quality of life and functioning,¹⁻³ is associated with increased mortality,⁴ and poses an economic burden.⁵

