Stress induction: **1. Baseline:** The Simple Reaction Task (SRT) will serve as a baseline for the stressor task. Participants press a key each time a number appears on the screen. The SRT has been used as a baseline for cognitive stressors in prior [name] lab studies; **2. Stress induction:** The Portland Arithmetic Stress Task (PAST)⁷⁰ is a cognitive stressor comprised of arithmetic problems titrated in difficulty. It has an adaptive failure algorithm, maintaining an error rate of ~40%. It has been shown to induce physiological stress across groups.⁷⁰⁻⁷²

Aim 3 – Quantitative data will be collected on paper and entered in REDCap by a study team member on an [name] lab computer and in-person clinical interview (i.e., Clinician-Administered PTSD Scale for DSM-5 [CAPS-5]). Using this data, we will examine sensitivity and responsiveness to change of outcomes. This Aim will be conducted in accordance with best practice guidelines,^{73,74} CONSORT recommendations,⁷⁵ and previous research.^{76,77} **Sensitivity** in both groups will be analyzed via relative efficiency; dividing the *F*-statistic for each physiological (systolic and diastolic BP) and self-report (psychological resilience and PTSD symptoms) by the largest *F*-statistic among outcomes (see Table below for measures).^{77,78} This process will clarify which outcomes are most sensitive to MBSR. To generate *F*-statistics for relative efficiency, we will conduct repeated measures ANOVAs for each outcome in both groups. **This statistical approach focuses on the degree to which measures are sensitive, not whether change is significant.** **Responsiveness to change** over time will be assessed in the MBSR group for physiological and self-report outcomes by: 1) calculating and comparing standardized mean response by subtracting baseline mean response from post-intervention mean response, and dividing by standard deviation of change^{74,79,80} and 2) examining zero-order correlations between a global impression of change measure (post-intervention) and change scores (baseline to post-intervention) for self-report outcomes.⁸¹⁻⁸³

Primary measures to be collected are listed below:

Method	Variable	Measurement Tool	Timepoints
Paper>REDCap	Psychological resilience	Brief Resilience Scale (BRS)	Pre, mid, post
Paper>REDCap	PTSD symptoms	PTSD Symptoms Checklist for DSM-5 (PCL-5)	Pre, mid, post
Paper>REDCap	Mindfulness	Five Facet Mindfulness Questionnaire (FFMQ-15)	Pre, mid, post

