Paper>REDCap	Perceived stress	Perceived Stress Scale (PSS-10)	Pre, mid, post
Paper>REDCap	Loneliness	UCLA Loneliness Scale	Pre, mid, post
Paper>REDCap	Distress	Distress tolerance scale	Pre, mid, post
Clinical interview	PTSD symptoms	Clinician-Administered PTSD Scale for DSM-5 (CAPS-5)	Pre, mid, post
CareTaker™	Physiological resilience	Blood pressure (BP)	Pre, mid, post

Stress induction: **1. Baseline:** The Simple Reaction Task (SRT) will serve as a baseline for the stressor task. Participants press a key each time a number appears on the screen. The SRT has been used as a baseline for cognitive stressors in prior [name] lab studies; **2. Stress induction:** The Portland Arithmetic Stress Task (PAST)⁷⁰ is a cognitive stressor comprised of arithmetic problems titrated in difficulty. It has an adaptive failure algorithm, maintaining an error rate of ~40%. It has been shown to induce physiological stress across groups.⁷⁰⁻⁷²

Interventions:

Mindfulness-Based Stress Reduction consists of weekly two-hour sessions for eight weeks, and a 7 hour retreat after Lab visit 3/week 8. The MBSR intervention will be facilitated by an experienced and

certified MBSR teacher. MBSR curriculum strongly encourages completion of home practice assignments (~30 minutes daily) to help integration of concepts into daily life. Participants will receive audio CDs and a DVD to help guide home practice.

Health and Wellness Education (HWE) Intervention is a didactic-based group intervention designed as an active comparator for randomized-controlled trials of MBSR. HWE provides instruction to participants regarding improving their emotional and physical health. In contrast to MBSR, there are no attempts to train participants' breathing, movement, or meditation habits or practices. HWE is administered in 8 weekly 2.5-hour classes with home practice to be completed between sessions (matched to MBSR for amount and effort). HWE also features one extended 7-hour retreat, similar to MBSR.⁸⁴ [name] (consultant) has conducted trials of MBSR among veterans with PTSD using a control group based on similar materials, and will provide mentorship to the PI in administering the control intervention. [name] and a trained RA will facilitate HWE.

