Sensitivity in both groups will be analyzed via relative efficiency; dividing the F-statistic for each physiological (systolic and diastolic BP) and self-report (psychological resilience and PTSD symptoms) by the largest F-statistic among outcomes (see Table above for measures).^{77,78} This process will clarify which outcomes are most sensitive to MBSR. To generate F-statistics for relative efficiency, we will conduct repeated measures ANOVAs for each outcome in both groups. This statistical approach focuses on the degree to which measures are sensitive, not whether change is significant. Responsiveness to change over time will be assessed in the MBSR group for physiological and self-report outcomes by: 1) calculating and comparing standardized mean response by subtracting baseline mean response from post-intervention mean response, and dividing by standard deviation of change^{74,79,80} and 2) examining zero-order correlations between

a global impression of change measure (post-intervention) and change scores (baseline to post-intervention) for self-report outcomes.⁸¹⁻⁸³

Qualitative data:

A thematic analysis approach⁶⁷ to qualitative data will explore participant experiences to understand feasibility, acceptability, and impact of assessments, protocol, and interventions.

Analysis process will consist of: 1) familiarization, 2) initial coding, 3) creating themes, 4) reviewing themes, 5) defining and naming themes, and 6) data interpretation.

9) Privacy, Confidentiality and Data Security

Standard institutional practices will be followed as described in the OHSU Information Security Directives (<http://www.ohsu.edu/xd/about/services/integrity/policies/ips-policies-info-sec-directiv.cfm#results>) to maintain the confidentiality and security of data collected in this study. Study staff will be trained with regard to these procedures. Any staff that will be involved in these research activities will have completed the requisite Human Subject Protection Training as required by the IRB prior to engagement.

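### Aim 3 reports signed change for the MBSR arm only and brings HWE in through unsigned F-statistics, so its specified output cannot tell MBSR-specific change from change that HWE shared, exceeded or reversed

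*Combined protocol and SAP*

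**What the plan says.** Section 8 (Data Analysis, Quantitative data) and the Aim 3 paragraph of section 6 (Procedures) give the same two analyses.

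- **Sensitivity**, in both groups. A repeated-measures ANOVA is run for each outcome, and each F is divided by the largest F among outcomes. The stated use is: "This process will clarify which outcomes are most sensitive to MBSR". The text adds that the interest is in how sensitive the measures are, not in significance. It does not say whether there is one ANOVA per arm or one model for both arms, nor which effect supplies the F.
- **Responsiveness**, restricted by arm: "Responsiveness to change over time will be assessed in the MBSR group for physiological and self-report outcomes by" two statistics. The first is a standardized mean response, obtained by "subtracting baseline mean response from post-intervention mean response, and dividing by standard deviation of change". The second correlates a global impression of change with "change scores (baseline to post-intervention) for self-report outcomes".

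Three other places bear on this. Aim 3 in section 2 says that "pre-post changes in physiological and psychological resilience and PTSD symptoms will provide crucial information regarding relationships between the intervention and changes in relevant variables", without limiting this to one arm. Section 6 (Interventions) describes HWE as a "didactic-based group intervention designed as an active comparator for randomized-controlled trials of MBSR". The Study Schedule in section 6 gives both arms the same questionnaires, CAPS-5 interview and blood pressure recording at three lab visits.

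**The concern.** The standardized mean response is the only signed summary of change over the intervention that the plan specifies, and it stops at one randomized arm. The conclusion drawn from Aim 3 is nevertheless specific to MBSR. Change in the MBSR arm alone includes whatever would have happened without MBSR, such as drift, repeat testing, and the attention and company of a weekly group. HWE is in the design to supply that reference, and its data are collected at the same visits.

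The ranking of outcomes is meant to inform a later mechanistic RCT. If an outcome ranks high because both arms moved together, or because HWE moved more, the later trial could be built around a measure that does not separate the arms. The specified output would give no warning of this.

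**Working it through.** The plan states no effect size, SD or power for Aim 3, so there is no figure of its own to reproduce. The check has three parts.

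**1. What is specified for HWE in section 8.**
- Recruitment and retention rates are compared between conditions, and home practice is correlated with attrition per condition. These are not outcome changes.
- Baseline-to-stressor t-tests on blood pressure are signed, but they compare task phases, are not split by arm, and do not concern change over the intervention.
- Repeated-measures F for each outcome has no sign.
- Standardized mean response and correlation with global impression of change are for MBSR only.

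No signed change over the intervention is specified for HWE, and no between-arm difference in change.

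**2. Whether the F-statistics can fill the gap.** F is a ratio of sums of squares, so reversing the direction of every change leaves it unchanged. Dividing by the largest F does not restore direction.

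*If F is the within-arm time effect.* Three-visit scores were simulated (assumed mean trend 0, −4, −8; between-subject SD 12; residual SD 7) and compared with their mirror image.

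| n in arm | F, original | F, mirror image | Standardized mean response, original | Mirror image |
|---|---|---|---|---|
| 10 | 1.83 | 1.83 | −0.45 | +0.45 |
| 8 | 2.94 | 2.94 | −0.78 | +0.78 |

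The same F fits improvement and equal worsening. The sizes depend on the assumed inputs; only the equality matters.

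*If F is group-by-time.* Exchanging the two arms leaves it unchanged: 0.147 both ways at 10 per arm and 2.41 both ways at 8 per arm in the simulated data. It measures how far the time courses differ but not which arm did better. For a symptom score where lower is better, with an MBSR baseline-to-post change of −0.5 SD of change (equal SD in both arms assumed):
- HWE +0.5: MBSR minus HWE = −0.5 − 0.5 = −1.0, MBSR better.
- HWE −1.5: MBSR minus HWE = −0.5 + 1.5 = +1.0, HWE better.

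The squared differences are equal, so with the same error variance a baseline-to-post interaction F is the same for two opposite conclusions.

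**3. Precision of the missing summaries.** Inputs: 20 participants (section 5a) allocated 1:1 (section 4), hence about 10 per arm. Section 3 cites average attrition of 21.3% in mindfulness trials for PTSD. This is background, not a planning figure. 20 × (1 − 0.213) = 15.7, or about 8 per arm.

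Half-widths of 95% intervals, in units of the SD of change (assumed equal across arms):
- Within an arm, t(n−1)/√n: 2.262/√10 = 0.72 at n = 10; 2.365/√8 = 0.84 at n = 8.
- Between arms, t(2n−2) × √(2/n): 2.101 × √0.2 = 0.94 at n = 10; 2.145 × √0.25 = 1.07 at n = 8.

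The statistic already planned is imprecise too. An MBSR standardized mean response of −0.5 at n = 10 has a 95% interval of −1.15 to 0.17 (noncentral t), and the plan attaches no interval to it.

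**The case against.** The strongest defence is that Aim 3 is a measurement aim in a 20-person feasibility study: "Using this data, we will examine sensitivity and responsiveness to change of outcomes". Responsiveness is usually assessed where change is expected, and the plan promises no treatment-effect estimate. This stands as a reason not to ask for an efficacy test. It does not explain leaving HWE out of the signed statistic when the conclusion is about sensitivity to MBSR in particular.

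Second, ANOVA software normally prints visit means by arm, and section 6 commits Aim 3 to CONSORT recommendations, so HWE direction may be reported anyway. This also stands. A reader might infer that the trial will be unable to say which way HWE moved. The documents do not support that: the data will exist, and the gap is in what section 8 commits to report.

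Third, under a group-by-time reading the F does measure how the arms differ. A reader might infer that the plan has no between-arm information on outcomes at all; given the ambiguous ANOVA wording, that goes too far. What is missing on that reading is direction and an estimate.

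Fourth, the between-arm interval would be close to one SD of change on either side. That is correct and limits what the added table can show. It argues for displaying the interval and labelling the table, not for omitting the comparator.

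**Conclusion.** The concern holds as a gap in the specified output. Sections 6 and 8 confine signed change to MBSR, leave HWE to F-statistics of unstated type, and then draw a conclusion about MBSR. On either reading of the ANOVA, the committed results cannot distinguish MBSR-specific change from change that HWE shared, exceeded or reversed. This rests on the text and on the algebra of F, not on any assumed effect size.

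It would be too much to conclude that a planned analysis is invalid, that the feasibility aims are affected, or that the plan has failed to deliver an efficacy comparison. It never undertook one. The half-widths of 0.94 and 1.07 SD assume equal SDs of change and 10 or 8 assessed per arm. At that precision the added estimates are descriptive. The change is worth making because it is cheap and because the ranking depends on a reference the trial already collects.

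**What to change.** In sections 6 and 8:

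1. For the standardized mean response, replace *in the MBSR group* with *in each arm*. The correlation with global impression of change can stay as it is.
2. For every outcome in the ranking (SBP, DBP, BRS, PCL-5 and CAPS-5), report the signed baseline-to-post mean change with 95% CI by arm, the MBSR-minus-HWE difference in change with 95% CI, and the number assessed in each arm. Label the table descriptive and not a test of efficacy. Baseline-to-mid changes are optional. Naming CAPS-5 is a minor clarification: section 6 and the measures table suggest it is intended, but section 8 does not name it.
3. State that the ranking of sensitivity to MBSR uses the group-by-time F, read together with the sign of the between-arm difference, so that an outcome on which HWE did better is not listed as sensitive to MBSR.

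The cost is a few sentences and one table from data already scheduled, with no new visit, measure or staff. The downside is the wide between-arm interval, which could be misread as an efficacy result if the label is dropped.

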Documentation of training will be held on secure password protected computers at OHSU. Prior to implementation of any protocol changes, amendments will be submitted to the OHSU Institutional Review Board for approval. [name] will be responsible for continuous data and safety monitoring of all participants, and discussion of any data or safety monitoring concerns will be a routine topic of mentorship and consultation meetings. In the event there are AEs/SAEs that require medical intervention, [name], a board-certified neurologist, will be available to review events and refer them as needed.

Paper files will be stored in locked filing cabinets in restricted access offices at OHSU and will not leave the [name] lab facility. Electronic data is stored on restricted drives on the OHSU network, on OHSU approved cloud location and on encrypted computers. Electronic data will also be stored in a custom database housed on an OHSU secure server. Access to data is restricted to study personnel. Access to data requires OHSU ID/password authentication.

Upon enrollment, participants will be assigned a code that will be used instead of their name, medical record number or other personally identifying information. Electronic files for data analysis will contain only the subject code. Codes will not contain any part of the 18 HIPAA identifiers (initials, DOB, MRN) The key associating the codes and the participants personally identifying information will be restricted to the PI and study staff. The key will be kept secure on a restricted OHSU network drive in a limited access folder.

BP will be collected via Caretaker Medical VitalStream™ device, which accurately and wirelessly measures vital signs. The VitalStream™ uses an automated readout inflatable finger cuff and is connected via Bluetooth to a tablet. The CareTaker™ is completely wireless, and will relay data via Bluetooth connectivity to a tablet. It allows for secure wireless monitoring via a real-time mobile application, or remote monitoring via a Cloud Portal. For the purposes of the study, we will monitor participant data via mobile application on an encrypted Android tablet in a room adjacent to the testing room during the laboratory stressor task. There is no storage, processing or transmission of any PHI or HIPAA identifiers through VitalStream. It does not connect to OHSU network, but is transmitted via Bluetooth to an encrypted tablet.

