At the completion of the study, if patients consent to sharing data in the repository, their data will be released to repository IRB #7436. See repository protocol for details about requesting, releasing, and labeling data.

10) Risks and Benefits

a) Risks to Subjects

The risk in participating in the present study is low. Participants may feel distress when reporting their PTSD symptoms or identifying their index trauma (i.e., the most salient trauma connected to their PTSD symptoms) as part of the administration of the Clinician-Administered PTSD Scale (CAPS-5). Participants may also feel discomfort or embarrassment when discussing their general experiences during the intervention conditions. They may also feel stress or frustration when completing the laboratory stressor paradigm. Participants have the right to withdraw, and may attend intervention groups and not actively participate, or may not complete MBSR home practice between sessions.

There is no discomfort associated with the collection of physiological data. The CareTaker™ device using a Velcro finger cuff attached with similar tightness to an arm cuff blood pressure monitor. A thin clear tube connects the finger cuff to a small wrist pack that houses the electronic components of the device. The CareTaker™ is completely wireless, and will relay data via Bluetooth connectivity to a tablet.

One of the potential risks of participation breach of confidentiality. It is possible that, if someone inadvertently obtained data, this could result in harm to research participants, with legal, financial, or emotional implications of the affected Veterans. We will take all possible measures to protect the security and integrity of personal health information.

b) Potential Benefits to Subjects

Veterans may find it rewarding to engage in group-based interventions in which they are encouraged to share their experiences with other veterans with similar struggles related to PTSD symptoms. They may similarly appreciate being able to share their perspectives regarding their ability and strategies for coping with symptoms. Participants may also experience reduction in symptoms of PTSD, depression, and anxiety as a result of participating in the MBSR condition.

REFERENCES

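### Psychological harms are named as risks but not defined as events, asked about on schedule or summarised, so they may be missed or recorded unequally between arms

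*Combined protocol and SAP*

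**What the plan says.** **Oversight.** Section 9 (Privacy, Confidentiality and Data Security) names one role that "will be responsible for continuous data and safety monitoring of all participants" and adds that "discussion of any data or safety monitoring concerns will be a routine topic of mentorship and consultation meetings". The next sentence makes a board-certified neurologist available to review events and refer them as needed, under the condition "In the event there are AEs/SAEs that require medical intervention". Neither AE nor SAE is defined.

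**Named risks.** Section 10a (Risks to Subjects) lists three that arise in study procedures:
- at the CAPS-5: "Participants may feel distress when reporting their PTSD symptoms or identifying their index trauma";
- in the groups: "Participants may also feel discomfort or embarrassment when discussing their general experiences during the intervention conditions";
- at the lab task: "They may also feel stress or frustration when completing the laboratory stressor paradigm".

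**Collection and analysis.** The measures table and Study Schedule in section 6 have no adverse-event row, form or question. Section 8 (Data Analysis) covers recruitment, retention, home practice, stress induction, sensitivity, responsiveness and thematic analysis. It does not mention harms.

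**Facilitators.** Under Interventions in section 6, MBSR is led by a "certified MBSR teacher". HWE is led by a named person and a trained research assistant, and a consultant "will provide mentorship to the PI in administering the control intervention". No duty to report events is stated for either set of facilitators.

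**The concern.** The review condition fits poorly with the protocol's own list of risks. The harms it expects from procedures are distress, discomfort and frustration, while the only clinical review it describes starts from a need for medical intervention. With no definition and no scheduled question, what gets recorded depends on who speaks up and who is listening, and the listeners in the group sessions differ by arm.

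This bears on the trial's aims. Aim 1 is to judge acceptability and differential retention in support of a larger trial. The Background cites average attrition of 21.3% in mindfulness-based interventions for PTSD, calls it much higher than in the general population, and says the reason is unknown. If exits here are not linked to recorded distress, this trial will have difficulty shedding light on that reason. Harm data that were not asked for at the time cannot be recovered in analysis.

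**Working it through.** The plan states no harm rate, detection rate or safety sample size, so it has no figure to reproduce. The main check is a comparison of sections, followed by a short illustration.

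**1. What could capture distress, and where it falls short**

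| Route | Section | Limit |
|---|---|---|
| Continuous monitoring and meetings | 9 | Gives a responsible role and a meeting topic, but no definition, question, timing or count |
| Neurologist review | 9 | Conditional on need for medical intervention |
| CAPS-5, PCL-5 and PSS-10 | 6, Study Schedule | Lab visit 1, week 5 and week 8 only; no rule turns a worse score into an event |
| Blood pressure referral | 7a | Blood pressure only; section 7a bases referrals on blood pressure values alone |
| Focus group, week 9 | 6, Aims 1&2 | Group discussion; listed topics do not name harms |
| PHQ-9 item 9 | Screening measures | Screening only; absent from the study-visit questionnaires |

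The retreat follows Lab visit 3, and the only scheduled activity after it is the focus group. So no symptom measure is scheduled after the longest single session. Section 8 mentions a post-intervention global impression of change, but the schedule does not place it and it is not a harm question.

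**2. What zero events would mean**

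Inputs from section 4 and section 5a: 20 participants allocated 1:1, so about 10 per arm. If everyone is asked and no one reports an event, the one-sided 95% upper bound on the per-person risk is 1 − 0.05^(1/n):
- n = 10: 1 − 0.05^(1/10) = 0.259
- n = 20: 1 − 0.05^(1/20) = 0.139

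These bounds treat asking as fully sensitive. If only a fraction s of events is detected, the bound applies to the recorded rate, and the true risk is bounded by that value divided by s. For n = 10:
- s = 0.8: 0.259/0.8 = 0.32
- s = 0.4: 0.259/0.4 = 0.65

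Under spontaneous reporting s is unknown, so no bound follows unless one is assumed.

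**3. What unequal detection could do (assumed inputs, illustration only)**

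Take a true rate of 30% in both arms of 10, with detection of 80% in one arm and 40% in the other. Which arm is which is left open.
- Expected recorded events: 10 × 0.30 × 0.80 = 2.4 and 10 × 0.30 × 0.40 = 1.2
- Chance that none is recorded: (1 − 0.24)^10 = 6.4% and (1 − 0.12)^10 = 27.9%

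With 80% detection in both arms the figures are 2.4 and 6.4% in each. Over assumed true rates from 10% to 50%, with 80% against 40% detection, expected recorded events run from 0.8 vs 0.4 to 4.0 vs 2.0. The approximate power of a two-sided 5% two-proportion comparison to show the artefact is about 6% to 16%. Unequal ascertainment could therefore be neither recognised nor excluded from the data.

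**The case against.** The strongest reply is that section 9 does not restrict safety oversight to medical events. The sentence before the review clause covers all participants continuously and takes any concern to routine meetings, and section 6 allows withdrawal to protect a participant from excessive risk. A reader might infer that a worsening of PTSD symptoms needing no medical care escapes review altogether. The documents do not support that: such distress is outside the neurologist clause, not outside oversight. What remains is that monitoring can discuss only what reaches it, and no procedure brings distress to it.

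A second reply is that both arms have the same interview and questionnaires at three visits, so a lasting deterioration would be measured. That is right. The gap concerns transient distress, events between visits, events after Lab visit 3, and people who leave before the later visits.

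A reader might also infer that detection will differ by arm, and that under-detection favours MBSR. Neither is shown. Two of the three named risks arise at lab visits that are identical in both arms, and the third is stated for both conditions. A reporting duty is missing for HWE facilitators as well as for the MBSR teacher. An experienced teacher might notice more distress than a research assistant, not less. Names are removed, so it cannot be confirmed whether the safety monitor also leads HWE. No between-arm harms comparison is planned, so no planned estimate is biased.

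Finally, this is a 20-person feasibility study that the protocol describes as minimal risk. That argues for a light remedy, not for none.

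**Conclusion.** The point holds in a limited form. The protocol has general safety oversight, but it lacks a definition of adverse events, a scheduled harm question and a harms summary, and its one named clinical review does not match the psychological risks it lists. Some distress will be recorded only if volunteered or noticed. Ascertainment may differ between arms, mainly for in-session and between-visit events, and the direction is unknown.

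The size of the problem cannot be estimated from the documents, which give no harm or detection rates; the 30%, 80% and 40% figures are assumptions. The gain from asking is that zero events among all those asked would bound the risk below about 26% per arm or 14% overall. This assumes about 10 per arm, every participant asked, and complete reporting when asked. The change is worth making before data collection because it is inexpensive and cannot be made afterwards.

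**What to change.** 1. Define adverse events for recording purposes so that they include psychological distress and symptom worsening, whether or not medical intervention is needed.
2. Reconcile the review wording in section 9 with the risks in section 10a. The clinical review rule itself is for the investigators to set.
3. Ask one identically worded open question in both arms at four existing contacts: the end of Lab visit 1, Lab visit 2, Lab visit 3, and week 9 after the retreat. At week 9 it should be put individually, not in the group discussion. Where possible, existing study staff who do not facilitate that participant's group should collect the answers.
4. Give both sets of facilitators the same duty to forward events raised in sessions.
5. In section 8, beside retention, report descriptively by arm the number of participants asked, the number with any event, and the number with an event leading to exit. No test is needed.

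**Cost:** a wording amendment, one form item and one descriptive table. At full attendance this is 4 × 20 = 80 short answers, with no added visits or staff. The downside is more minor events to log.
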